6.3.2. Sleep Quality VAS

A repeated measures model (see Section 4.7) will be used to model Sleep Quality VAS total score. Model based LS mean estimates will be provided for the following:

- mean score by study treatment (75/2.5 dose, 37.5/2.5 dose, placebo),

- difference in mean score between study treatments (75/2.5 dose vs placebo, 37.5/2.5 dose vs placebo, and 75/2.5 dose vs 37.5/2.5 dose) with 95% confidence intervals and respective p-values (for null hypothesis).

Summary statistics of Sleep Quality VAS total score by study treatment and a by-participant listing will also be provided.

6.3.3. PSG sleep and arousal parameters and alternate measures of AHI, ODI, and HB

Descriptive statistics for the reported value and change from baseline by study treatment will be reported for sleep stages distribution and percentage of time in the various sleep stages (SE, WASO, NAW, SOL, Stage N1%, Stage N2%, Stage N3%, Stage R%). A 95% confidence interval will be included for the change from baseline.

Snoring index, arousal indices (respiratory and spontaneous), fraction of hypopneas (see below) and alternate measures of AHI, ODI, and HB (AHI[4%]: in NREM sleep, in REM sleep, AHI adjusted for position [see below]; AHI[3% or arousal]; HB[3% or arousal]; HB[Total]; ODI[3%]) and will have results provided similar to Section 6.1 (including the model of change from baseline and the descriptive statistics).

Additional clarifying details for the analysis of some of these endpoints is as follows:

- Fraction of hypopneas will be calculated by using the number of hypopneas divided by the total number of apneas plus hypopneas.
- AHI adjusted for position: An additional covariate of % time supine (%TS) will be added to the repeated measures model for AHI(4%).

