7.2 Safety Assessments

- Planned time points for all safety assessments are provided in the SoA.
- Safety monitoring will be guided by the established safety profiles of atomoxetine and
 oxybutynin, and by Phase 1 and 2 safety data for the combination. Safety assessments will
 include physical examinations, measurement of vital signs, monitoring and recording of AEs,
 SAEs, and pregnancies, recording of study or treatment discontinuations. Effects on OSA and
 sleep parameters (e.g., sleep time and sleep stages) will also be monitored by PSG.
- Adverse events of special interest include effects on urine outflow, as both atomoxetine and oxybutynin are associated with urinary retention. Effects of atomoxetine on heart rate and blood pressure are expected to be modest, as indicated by the initial data described above, and will also be monitored. Participants with serious cardiac abnormalities will be excluded from the study. Suicidal ideation in children and adolescents is a boxed warning for atomoxetine; however, analysis in adult patients, the target population for the proposed OSA study, did not reveal an increased risk of suicidal ideation or behavior in association with atomoxetine. Daytime sleepiness is both a potential safety outcome and efficacy outcome in OSA. Both atomoxetine and oxybutynin may be associated with somnolence, and oxybutynin is additionally associated with anticholinergic CNS effects such as memory difficulty.

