3. INVESTIGATIONAL PLAN

3.1. Study Design

[figure not shown]
Study APC-004 is a randomized, double blind, placebo-controlled, 3-period, single-dose crossover study in patients with mild-to-moderate OSA. A screening visit and polysomnographic (PSG) exam will be conducted to establish that each participant meets study enrollment criteria. Each participant will then receive a single dose of each of the following during 3 overnight PSG exams, each separated by a one week washout period:

- A: Atomoxetine 75 mg + R-oxybutynin 2.5 mg (i.e., 75/2.5)
- B: Atomoxetine 37.5 mg + R-oxybutynin 2.5 mg (i.e., 37.5/2.5)
- C: Placebo

Efficacy and safety endpoints will compare the 75/2.5 and 37.5/2.5 doses to each other and to placebo.

Each PSG night is followed by a 1-week washout period. Adverse event (AE) and serious adverse event (SAE) information is recorded at each study visit and by telephone contact with participants during each washout period. The overall study duration will be up to 12 weeks (see Figure 1).

Figure 1: Overview of Study Design

PSG = polysomnography.

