4.6. Data Derivations and Transformations

Study Day will be calculated as:

- Date of assessment – date of randomization + 1 for assessments done on or after date of randomization
- Date of assessment – date of randomization for assessments done before date of randomization

For each efficacy and safety endpoint, the baseline value will be calculated as the last non-missing value prior to randomization (except where unscheduled assessments are performed the baseline value should be the value recorded at Screening). Where applicable, change from baseline values will be calculated as:

Change from Baseline = assessment value – baseline value,

while the percent change from baseline values will be calculated as:

$$\text{percent change from baseline} = \frac{\text{change from baseline}}{\text{baseline value}} \times 100\%.$$

For the endpoints that look for the proportion of participants with $\geq 50\%$ reduction, participants will be assigned a visit level indicator:

$$\text{Indicator of } \geq 50\% \text{ reduction} = \begin{cases} 1 & \text{if percent change from baseline } \leq -50\% \\ 0 & \text{otherwise} \end{cases}.$$

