6.1. Primary Efficacy Analysis – HB(4%)

Multiple comparisons will be performed as described in Section 4.5. A repeated measures model (see Section 4.7) will be used to model change in $\log_{10}(\text{HB}[4\%] + 1)$ from baseline. Model based LS mean estimates will be provided for the following:

- mean change by study treatment (75/2.5 dose, 37.5/2.5 dose, placebo),

- difference in mean change between study treatments¹ (75/2.5 dose vs placebo, 37.5/2.5 dose vs placebo, and 75/2.5 dose vs 37.5/2.5 dose) with 95% confidence intervals and respective p-values (for null hypothesis).

If the model shows there is a visit (i.e., period) effect, then ad hoc analyses will be performed. A sensitivity analysis will be performed using the PP Set on the primary efficacy endpoint using the same methods described above and using HB(4%) with identity transform (i.e., without transform) on the mITT set.

Descriptive statistics for the reported value and change from baseline in $\log_{10}(\text{HB}[4\%] + 1)$ will be presented by study treatment. By taking the inverse transformations of the respective means, the geometric mean of HB(4%) + 1 and the ratio of the geometric mean to baseline will be reported.

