7.6. PSG Parameters

PSG safety data will be summarized by presenting descriptive statistics of actual values and changes from baseline by study treatment. PSG safety parameters include total sleep time, heart rate, and total time with $\text{SaO}_2 < 90\%$. A by-participant listing of PSG parameters (including baseline and efficacy parameters) will also be provided.

² In the case that the total correct is 0, the participant will be dropped from the model.

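### Sleep continuity, sleep stages, total sleep time and PSG heart rate have no planned within-participant contrast with placebo or between doses; the only interval specified is on change from the screening night

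*SAP*

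**What the plan says.** The comparative aim is explicit. SAP 2.1.1 makes comparison of the two doses with each other and with placebo the primary objective, for efficacy and safety, and SAP 3.1 says: "Efficacy and safety endpoints will compare the 75/2.5 and 37.5/2.5 doses to each other and to placebo".

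The analysis of the PSG measures then divides:

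- **Sleep continuity and stages (SAP 6.3.3, first paragraph).** This covers sleep efficiency (SE), WASO, number of awakenings (NAW), sleep onset latency (SOL) and Stage N1, N2, N3 and R%. The plan is: "Descriptive statistics for the reported value and change from baseline by study treatment will be reported for sleep stages distribution" and the related measures, followed by "A 95% confidence interval will be included for the change from baseline". No model is named.
- **Total sleep time and PSG heart rate (SAP 7.6).** "PSG safety data will be summarized by presenting descriptive statistics of actual values and changes from baseline by study treatment". No interval is specified.
- **Snoring, arousal indices, fraction of hypopneas and the alternate AHI, ODI and HB measures (SAP 6.3.3, second paragraph).** These are analysed as in SAP 6.1, which provides the "difference in mean change between study treatments" for all three treatment pairs.
- **Time with SaO2 below 90% (SAP 6.2.4).** This is also listed in SAP 7.6, but it is modelled with all three contrasts.

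Baseline is defined in SAP 4.6: "the baseline value will be calculated as the last non-missing value prior to randomization". For PSG measures the schedule of activities makes this the V2 screening night. Protocol 7.2, under safety, says that "sleep parameters (e.g., sleep time and sleep stages) will also be monitored by PSG".

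**The concern.** V2 always comes first, no tablet is given, and it takes no part in the randomised treatment order. A change from V2 on a drug night is therefore the drug effect plus whatever else differs between V2 and the later laboratory nights. The randomised placebo night shares that second component, and a within-participant contrast with it removes the shift. For these ten measures no such contrast is planned.

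Two misreadings follow. If sleep differs between V2 and later nights for reasons unrelated to drug, an interval excluding zero on a drug row looks like a drug effect. If the shift and a drug effect run in opposite directions, a real effect can look like no change.

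This matters beyond the tertiary tables. Protocol 7.2 places sleep time and stages under safety monitoring, SAP 6.3.3 analyses AHI separately in REM and NREM sleep, and SAP 4.4.1 drops most PSG indices for nights with under 120 minutes of sleep. An effect on sleep time or stage would bear on how the efficacy results are read.

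**Working it through.** The plan gives no precision or power figure for any of these measures; the SD of 9 in SAP 9 is for HB. The check is therefore in units of the within-participant SD of one night, SDw.

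**Inputs**

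- Participants: 30 entered (Protocol 8.1, SAP 9). At the 20% discontinuation limit, 30 × 0.8 = 24.
- Shift between V2 and later nights, s, in SDw units: not in the documents. Assumed range 0 to 1.0.
- Also assumed: equal SDw on every night, independent night-to-night errors, and a shift common to all treatments.

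**Step 1. Standard errors.**
Change from V2 on one treatment: SE = SDw × √(2/n).
Drug minus placebo, within participant: SE = SDw × √(2/n).
The two are equal, so under these assumptions the placebo contrast costs no precision. The 95% half-width is t(0.975, n−1) × √(2/n): 2.069 × 0.289 = 0.60 SDw for n = 24, and 2.045 × 0.258 = 0.53 SDw for n = 30.

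**Step 2. How often the planned interval excludes zero when the drug does nothing.**
The one-sample t statistic on change from V2 has noncentrality s / √(2/n) = s × √(n/2). For s = 0.5 this is 0.5 × √12 = 1.73 (n = 24) or 0.5 × √15 = 1.94 (n = 30). The two-sided rejection probability from the noncentral t distribution is:

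| Assumed shift s (SDw) | Planned interval excludes 0, n = 24 | n = 30 | Placebo contrast |
|---|---|---|---|
| 0 | 5% | 5% | 5% |
| 0.25 | 13% | 16% | 5% |
| 0.5 | 38% | 47% | 5% |
| 0.75 | 70% | 80% | 5% |
| 1.0 | 91% | 96% | 5% |

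The last column stays at 5% because a shift common to drug and placebo nights cancels in the difference.

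**Step 3. What the planned tables already contain.**
For a participant with all nights, (drug − V2) − (placebo − V2) = drug − placebo. Subtracting the tabulated placebo mean from a dose mean therefore gives a point difference free of V2 in completers. It comes with no standard error or interval, and it is not adjusted for visit or for unequal dropout.

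**Step 4. What the contrast could show.**
The difference detectable with 80% power is (1.960 + 0.842) × √(2/n): about 0.81 SDw for n = 24 and 0.72 SDw for n = 30.

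**The case against.** The strongest defence is that these are tertiary or safety measures, that SAP 7 declares the safety analyses descriptive, and that Protocol 7.2 promises monitoring and not a test. The placebo row sits beside the dose rows, so a common V2 shift would show there with its own interval, and a by-eye difference already removes V2. Much of this stands, and it limits the weight of the point. It does not supply the interval on the difference. Nor does the descriptive rule explain the omission: SE, WASO, NAW, SOL and the stage percentages are efficacy endpoints under SAP 2.2.3, and within SAP 7 the DSST is modelled with treatment ratios and 95% intervals. Sleep Quality VAS, snoring and the arousal indices are modelled as well.

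A reader might infer more than the documents support:

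- *That these measures are reported only as change, with the placebo night unused.* SAP 6.3.3 and 7.6 also tabulate the values themselves by treatment, and placebo is one of the treatments.
- *That PSG safety measures are never compared.* Time with SaO2 below 90% has all three contrasts in SAP 6.2.4.
- *That the crossover cannot show an effect on sleep.* The data fully support the contrast. The gap is in the planned output.
- *That selection at V2 biases these measures directly.* The PSG entry criterion is AHI 5 to 20, not sleep continuity or stages.

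It is also fair that the size rests on an assumed shift. With no shift the planned interval behaves nominally, and complete masking of a drug effect needs a shift equal and opposite to it, which is a worst case.

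**Conclusion.** The point holds as a gap in the planned analysis. Eight sleep measures in SAP 6.3.3 and two in SAP 7.6 have no planned within-participant estimate or interval for dose versus placebo or dose versus dose, although SAP 2.1.1 and 3.1 state that aim. The only interval specified, for the eight, answers a different question and can mislead. With no drug effect it excludes zero in 5% of trials if V2 resembles later nights, 13–16% at a shift of 0.25 SDw, 38–47% at 0.5 and 70–80% at 0.75, against 5% for the placebo contrast. Those figures assume equal variances, independent night errors and a shift common to all treatments. The documents neither establish nor exclude any shift. The primary and secondary analyses, including time with SaO2 below 90%, are unaffected. This is a worthwhile, inexpensive improvement and not a flaw in the design.

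**What to change.** In SAP 6.3.3, extend the SAP 4.7 treatment-plus-visit model to SE, WASO, NAW, SOL and Stage N1, N2, N3 and R%. In SAP 7.6, do the same for total sleep time and PSG heart rate. For each, report the LS mean differences for 75/2.5 versus placebo, 37.5/2.5 versus placebo and 75/2.5 versus 37.5/2.5 with 95% intervals, labelled exploratory and unadjusted. Estimates with intervals suffice; p-values are not needed. State how distributional fit will be checked for counts and latencies (NAW, SOL, WASO), and name an alternative, such as a log scale, before unblinding.

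Keep the change-from-baseline tables as descriptive, with a note that their interval is not a treatment effect.

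The cost is SAP wording and about ten more runs of a model already needed elsewhere, with no new data or participants. The downside is 10 measures × 3 contrasts = about 30 further unadjusted contrasts. Some overlap: the stage percentages share a denominator, and with a fixed 8 hours in bed (Protocol 7.1.1) SE and total sleep time carry nearly the same information. The report should say so.

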7. SAFETY ANALYSIS

Safety assessments will include measurement of adverse events (AEs) and serious AEs (SAEs).

The analyses will be descriptive and will be based on the Safety Set. The safety assessments will be summarized by the study treatment the participant actually received within each period.

7.1. Extent of Exposure

The number and percentage of participants receiving study treatment will be summarized by study treatment and overall. A by-patient listing will be provided.

7.2. Adverse Events

An AE is any untoward medical occurrence in a participant or clinical study participant, temporally associated with the use of a study treatment, whether or not considered related to the medicinal product.

An AE can therefore be any unfavorable and unintended sign (including an abnormal laboratory finding), symptom, or disease (new or exacerbated) temporally associated with the use of a study treatment.

7.2.1. Treatment-emergent Adverse Events

A treatment-emergent adverse event (TEAE) is defined as any event not present prior to exposure

of study drug or an event already present that worsens in either severity or frequency following exposure. Each TEAE is assigned to the most recent study treatment administered on or before the TEAE's date of onset.

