7.3.1 Time Period and Frequency for Collecting AE and SAE Information

All AEs and SAEs will be collected from randomization until the end of the study at the timepoints specified in the SoA.

All SAEs will be recorded and reported to the Sponsor or designee within 24 hours, as indicated in Appendix 3. The Investigator will submit any updated SAE data to the Sponsor within 24 hours of it being available.

Investigators are not obligated to actively seek AEs or SAEs after the conclusion of study participation. However, if the Investigator learns of any SAE, including a death, at any time after a participant has been discharged from the study, and he/she considers the event to be reasonably related to the study treatment or study participation, the Investigator must promptly notify the Sponsor.

The method of recording, evaluating, and assessing causality of AEs and SAEs and the procedures for completing and transmitting SAE reports are provided in Appendix 3.

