- Exacerbation of a chronic or intermittent pre-existing condition including either an increase in frequency and/or intensity of the condition.
- New conditions detected or diagnosed after study treatment administration even though it may have been present before the start of the study.
- Signs, symptoms, or the clinical sequelae of a suspected drug-drug interaction.
- Signs, symptoms, or the clinical sequelae of a suspected overdose of either study treatment or a concomitant medication. Overdose per se will not be reported as an AE/SAE unless it is an intentional overdose taken with possible suicidal/self-harming intent. Such overdoses should be reported regardless of sequelae.
- "Lack of efficacy" or "failure of expected pharmacological action" per se will not be reported as an AE or SAE. Such instances will be captured in the efficacy assessments. However, the signs, symptoms, and/or clinical sequelae resulting from lack of efficacy will be reported as an AE or SAE if they fulfill the definition of an AE or SAE.

Events NOT Meeting the AE Definition

- Any clinically significant abnormal laboratory findings or other abnormal safety assessments which are associated with the underlying disease, unless judged by the Investigator to be more severe than expected for the participant's condition.
- The disease/disorder being studied or expected progression, signs, or symptoms of the disease/disorder being studied, unless more severe than expected for the participant's condition.
- Medical or surgical procedure (e.g., endoscopy, appendectomy): the condition that leads to the procedure is the AE.
- Situations in which an untoward medical occurrence did not occur (social and/or convenience admission to a hospital).
- Anticipated day-to-day fluctuations of pre-existing disease(s) or condition(s) present or detected at the start of the study that do not worsen.

Definition of SAE

If an event is not an AE per definition above, then it cannot be an SAE even if serious conditions are met (e.g., hospitalization for signs/symptoms of the disease under study, death due to progression of disease).

An SAE is defined as any untoward medical occurrence that, at any dose:

Results in death

Is life-threatening

The term 'life-threatening' in the definition of 'serious' refers to an event in which the participant was at risk of death at the time of the event. It does not refer to an event, which hypothetically might have caused death, if it were more severe.

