- There may be situations in which an SAE has occurred and the Investigator has minimal information to include in the initial report to the CRO. However, it is very important that the Investigator always make an assessment of causality for every event before the initial transmission of the SAE data to the CRO.
- The Investigator may change his/her opinion of causality in light of follow-up information and send an SAE follow-up report with the updated causality assessment.
- The causality assessment is one of the criteria used when determining regulatory reporting requirements.

Follow-up of AE and SAE

- The Investigator is obligated to perform or arrange for the conduct of supplemental measurements and/or evaluations as medically indicated or as requested by the CRO to elucidate the nature and/or causality of the AE or SAE as fully as possible. This may include additional laboratory tests or investigations, histopathological examinations, or consultation with other health care professionals.
- If a participant dies during participation in the study, the Investigator will provide the CRO with a copy of any post-mortem findings including histopathology.

- New or updated information will be recorded in the originally completed eCRF.
- The Investigator will submit any updated SAE data to the CRO within 24 hours of receipt of the information.

Reporting of SAE to CRO

SAE Reporting to CRO Via EDC Tool

- The Investigator must report any SAEs to the CRO within 24 hours of becoming aware of the event.
- When calling to report an SAE, state that you are reporting an SAE and give the Investigator's name, your name, the telephone number where you can be reached, and the protocol number and title.
- The Investigator and the Sponsor (or Sponsor's designated agent) will review each SAE report and the Sponsor/CRO will evaluate the seriousness and the causal relationship of the event to study treatment. In addition, the Sponsor (or Sponsor's designated agent) will evaluate the expectedness according to the reference documents (Investigator's Brochure or US product labeling for atomoxetine or oxybutynin). Based on the Investigator and Sponsor's assessment of the event, a decision will be made concerning the need for further action.
- After the study is completed at a given site, the electronic data collection tool will be taken off-line to prevent the entry of new data or changes to existing data.

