7.2.5. Adverse Event Summaries

Adverse event data will be displayed in listings by participant. The number and percentage of participants with AEs will be tabulated by SOC and PT. A participant with multiple AEs within a SOC or PT will be counted once toward the total for the total for the SOC or PT.

All AEs (serious and non-serious) occurring after completion of the informed consent process and before the end of study, regardless of relationship to study drug, will be included and presented by MedDRA SOC and PT.

For TEAEs, the following will be summarized by study treatment and presented for the Safety Set.

- i. An overall summary of TEAEs, which includes:
 - a. the number and percentage of participants experiencing any TEAE
 - b. the number and percentage of participants experiencing any TEAE by strongest relationship to study medication
 - c. the number and percentage of participants experiencing any TEAE by greatest intensity
 - d. the number and percentage of participants experiencing any TESAE
- ii. the number and percentage of participants experiencing any TEAE by SOC, PT
- iii. the number and percentage of participants experiencing any TEAE by SOC, PT and the greatest intensity
- iv. the number and percentage of participants experiencing any TEAE by SOC, PT and the strongest relationship to study medication
- v. the number and percentage of participants experiencing any TEAE leading to study discontinuation by SOC and PT.

In the overall summary of AEs table, besides tabulating the number and percentage of participants, the total number of AE episodes will also be provided. If a participant has repeated episodes of a particular AE within a treatment period, all episodes will be counted in the summary table and displayed by treatment.

For displays by SOC and PT, each participant will be counted only once per SOC and PT within each treatment.

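### SAP 7.2.1 attributes a worsening adverse event by onset date alone, so worsening after a later dose can be tabulated under the earlier treatment (minor)

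*SAP*

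**What the plan says.** **Definition and attribution (SAP 7.2.1).** An event is treatment-emergent if it was absent before exposure, or if it is "an event already present that worsens in either severity or frequency following exposure". The next sentence attributes every such event: "Each TEAE is assigned to the most recent study treatment administered on or before the" date of its onset. No date of worsening is mentioned.

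**Recording (Protocol 9.3, Appendix 3).** Under follow-up of AEs and SAEs: "New or updated information will be recorded in the originally completed eCRF". The same appendix lists among the events that qualify as an AE: "Exacerbation of a chronic or intermittent pre-existing condition including either an increase in frequency and/or intensity of the condition".

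**Collection period.** Protocol 7.3.1 states: "All AEs and SAEs will be collected from randomization until the end of the study". SAP 7.2.5 tabulates a wider set: "All AEs (serious and non-serious) occurring after completion of the informed consent process and before the end of study".

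**Tables affected (SAP 7.2.5).** The by-treatment TEAE summaries include "the number and percentage of participants experiencing any TEAE by greatest intensity", with parallel summaries by strongest relationship and by system organ class and preferred term. The opening of SAP Section 7 says that safety results are shown by the treatment actually taken in each period.

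**The concern.** The definition and the attribution rule do not fit each other. The definition accepts worsening as the reason an event is treatment-emergent, yet the only date that decides the treatment column is onset. In a three-period crossover the two dates can fall in different periods. If the record keeps its first onset date and is updated to a higher intensity, the whole event, including the part that appeared after the later dose, is counted in the earlier column.

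The comparison of safety between the two doses and with placebo is part of the primary objective in SAP 2.1.1, and the by-treatment TEAE tables carry much of it. With 30 participants, one severe event in the wrong column is visible.

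**Working it through.** The documents give no figure for this point, so there is nothing to reproduce. The check applies the rule as written and then counts.

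**Inputs.** Six sequences (ABC, ACB, BAC, BCA, CAB, CBA; A = 75/2.5, B = 37.5/2.5, C = placebo), in 5 blocks with one participant per sequence, so 5 per sequence (SAP 3.2.1). Washouts of at least 7 days (Protocol 1.2). N = 30 and discontinuation below 20% (Protocol 8.1), so 30 × 0.8 = 24 as the planning floor for completers. Dose days 1, 8 and 15 are assumed for illustration.

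**Step 1: the rule on dates.** The rule picks the last dose on or before onset.
- AE starts on day 2 and worsens on day 9. By onset it goes to the period 1 treatment. By date of worsening it would go to the period 2 treatment.
- AE dated day 0, worsening on day 2. By onset no treatment qualifies. By date of worsening it would go to the period 1 treatment.
- AE dated day 1, the first dosing day. It goes to the period 1 treatment, because the rule includes the day of dosing.

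**Step 2: how often each order occurs in adjacent periods.**
- Placebo directly before 75/2.5: BCA, CAB = 2 of 6, or 2 × 5 = 10 of 30 participants.
- Placebo directly before 37.5/2.5: ACB, CBA = 2 of 6, or 10 of 30.
- Placebo directly before an active dose: 2 + 2 = 4 of 6, or 20 of 30.
- An active dose directly before placebo: ABC, ACB, BAC, BCA = 4 of 6, or 20 of 30.

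Each of the six ordered pairs occurs in 2 of 6 sequences, so the design itself favours neither direction.

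**Step 3: effect of one event.** Take a mild AE that starts after placebo, is still present at the next dose, and becomes severe after 75/2.5. Assume that the participant has no other TEAE on 75/2.5.

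| Row | Rule as written: placebo / 75/2.5 | Worsening as a separate TEAE: placebo / 75/2.5 |
|---|---|---|
| Any TEAE | 1 / 0 | 1 / 1 |
| Severe | 1 / 0 | 0 / 1 |

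- Any TEAE: placebo does not change, because the mild event really did begin there. The 75/2.5 column gains 1/30 = 3.3 points, or 1/24 = 4.2 points with 24 completers.
- Severe: placebo loses one and 75/2.5 gains one, so the difference moves by 2/30 = 6.7 points, or 2/24 = 8.3 points. The strongest-relationship rows can behave in the same way.

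**Step 4: does other text close the gap?** The rule on incomplete dates in SAP 7.2.5 covers missing parts of an onset date only. Its rule on repeated episodes covers episodes within one treatment period, not an event carried into the next. Neither document says that a rise in severity or frequency opens a new record.

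**The case against.** The best reply is that the rule may already work. The SAP speaks of the onset of the TEAE and does not say first onset. For an event that becomes treatment-emergent by worsening, this can be read as the start of the worsening. Protocol Appendix 3 treats exacerbation of a pre-existing condition as an AE in its own right. The instruction to update the existing eCRF sits among follow-up items such as extra tests and post-mortem findings, and detailed data entry is left to a site training manual (Protocol 9.1.5) that is not among the documents. All of this stands: that the first onset date is kept is the literal reading, not an explicit instruction. It does not close the gap, because the exacerbation text does not clearly cover an AE that began on study and worsened after a later dose, and the only recording instruction in view points to the old record.

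Three further points stand and limit the size. The AE must still be present at the next dosing night, at least 7 days after a single dose, and then worsen. The safety analysis is descriptive. The listings show sequence, onset and resolution dates, so an AE that spans two doses can be seen, although the planned listing has no date of worsening.

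A reader might also infer that such events drop out of the by-treatment tables altogether. That is supported only for an AE dated before the first dose day. AE collection starts at randomization, which the Schedule of Activities places at the first dosing visit, and a pre-existing condition that worsens after dosing would normally be a new AE with a post-dose onset. The narrow case survives because the SAP tables admit events from consent.

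**Conclusion.** The point holds as a minor inconsistency. Applied literally, SAP 7.2.1 leaves a worsening that follows a later dose under the earlier treatment, together with its intensity and relationship. Per event, the later treatment's any-TEAE percentage is understated by up to 3.3 points (4.2 with 24 completers). The two-column movement of 6.7 (8.3) points is confined to intensity or relationship rows.

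These figures assume that the first onset date is kept, that the column denominator is 30 or 24, and that the participant has no other TEAE counted in the same row of the later treatment. The documents give no rate for such events; few are likely after single doses separated by at least a week.

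A reader might conclude that the rule systematically hides harm from the active doses. The documents do not support that. An event can equally move from placebo to an active column, and between the two doses the effect is to blur the dose comparison. Nor should every sequence with placebo somewhere before 75/2.5 be given equal weight: in CBA the AE would have to last through two washouts and an intervening dose.

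**What to change.** In SAP 7.2.1, state that any increase in severity or frequency of an ongoing AE after a later dose counts as a separate TEAE, is dated from the worsening, and is assigned to the most recent treatment taken before the worsening. The first event stays under the earlier treatment at its pre-worsening intensity.

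The sentence must cover every ongoing AE. If it were limited to events that are treatment-emergent only because they worsened, it would miss the example above, where the event was already a TEAE when it began after placebo.

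Align the AE recording instruction, so that such a worsening is entered as a new record with its own start date and not as an update of the old one.

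The cost is one sentence in the SAP and one in the recording instruction, made before database lock. The downside is a few split AE records, which slightly raise the count of AE episodes. Priority: low.
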